12.5 Secondary Analysis

Aim 2 (Secondary): To evaluate efficacy of the BBT-I in treating cancer-related symptoms such as cancer-related fatigue and cognitive difficulties in breast cancer patients receiving chemotherapy.

Hypothesis 2 (Secondary): BBT-I compared to an attention control group will be associated with greater improvements in fatigue and cognitive difficulties (as measured by the Brief Fatigue Inventory, and our Cognitive Battery that includes neuropsychological testing) from baseline through the 12 month follow up.

Aim 3 (Secondary): To examine potential moderators and mediators of BBT-I intervention effects on insomnia, cognitive difficulties, and fatigue. In particular, we are interested in age, depression and anxiety, emotion regulation and side effects (hot flashes) as potential moderators of the intervention effects as well as evaluating modifiable behavioral and physiological mechanisms as hypothesized mediators.

Hypothesis 3 (Secondary): In women with breast cancer receiving chemotherapy, intervention effects on insomnia, fatigue, and cognitive difficulties will be mediated by select behavioral mechanisms [i.e., maladaptive sleep behaviors (The Sleep Behavior Self-Rating Scale, sleep diaries, actigraphy), dysfunctional beliefs and attitudes (Dysfunctional Beliefs and Attitudes about Sleep) and physiological mechanisms [i.e., dysregulated circadian rhythms (measured by salivary cortisol), disrupted sleep wake cycles (actigraphy), and autonomic tone (RSA)].

As hypothesized mediators, we will carefully examine behavioral (measured by DBAS, SBSRS and sleep diaries) and physiological mechanisms (measured by HRV, salivary cortisol and actigraphy). Examination of moderators will be exploratory. As potential moderators, we will examine age, baseline anxiety and depression, baseline emotion regulation and baseline hot flashes. Among these potential moderators, some will not be qualified as moderators but predict outcome regardless of the intervention assignment status (we will classify these as non-specific predictors of the outcome). For the moderator/mediator investigation, we will apply the McArthur framework.^{98,99} Our analysis strategy in detecting moderators and mediators is mixed effects modeling, where the McArthur approach will be embedded.

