12.6.2 Sample size justification

For the primary Hypothesis 1 (BBT-I will show greater reduction of insomnia symptoms measured by ISI from baseline to the 12-month follow-up compared to the control), we estimated power in the proposed mixed effects modeling framework fully accounting for the longitudinal study design and projected attrition rate. The primary outcomes, ISI, will be measured at baseline, 6 weeks (end of treatment), 30 weeks, and 58 weeks (primary end point). For our power estimation, we used ML based mixed effects modeling assuming a linear trend. We assumed that at least 60% of variance is explained by the growth model for the primary outcome (i.e., reliability of 0.6), given that previous studies reported reliability ranging from 0.65-0.83.^{105,106} For attrition, we assumed gradually increasing attrition over time, resulting in 25% attrition by the 6-month follow-up assessment. We assumed a medium effect size, Cohen's d of 0.4 to 0.6, based on a previous study.¹⁰⁷ We also consider this range of effect size as the lower bound of a clinically meaningful treatment effect. Under this scenario, the estimated power to detect the group difference in change in ISI is 0.88-0.99 ($d=0.4$ to 0.6 , $\alpha=.05$, two-tailed) with $N=180$ (90 BBT-I, 90 control). We estimated power for the secondary Hypothesis 2 (BBT-I compared to the control will show greater improvements in fatigue and cognitive difficulties) using the same mixed effects modeling strategy. We assumed a moderate effect size of $d = 0.35$ to 0.4 , based on a previous study.^{108,109} We do not adjust for testing of multiple outcomes given that fatigue and cognitive difficulties are secondary outcomes. Under this scenario with reported reliability of 0.67 and higher,^{108,109} the estimated power to detect the group difference in change in BFI is 0.84-0.91 ($d=0.35$ to 0.4 , $\alpha=.05$, 2-tailed). For the mediator Hypothesis 3, we estimated power focusing on the main effect of the mediator on the outcome.^{98,99} We assumed a

Behavioral Intervention for Insomnia in Cancer

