moderate correlation between the hypothesized mediators and the outcome ($r=0.2$ to 0.3). We do not adjust for testing of multiple mediators given our concerns in failing to detect possible mediators due to insufficient power (note that our trial is powered based on our primary hypothesis). Under this scenario, the estimated power to detect the mediation effect is $0.76-0.99$ ($r=0.2$ to 0.3 , $\alpha=.05$, two-tailed). For all hypotheses, we will carefully monitor both statistical (i.e., p-value) and clinical (i.e., effect size) significance, with more emphasis on clinical significance in the secondary hypotheses.

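### The 0.76-0.99 given for Hypothesis 3 is power for the mediator-outcome association, not power to detect mediation

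*Combined protocol and SAP*

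**What the plan says.** Section 12.5 states Hypothesis 3 as a secondary hypothesis: "intervention effects on insomnia, fatigue, and cognitive difficulties will be mediated by select behavioral mechanisms", and by physiological mechanisms. On method it says: "For the moderator/mediator investigation, we will apply the McArthur framework", embedded in mixed effects modelling. It prints no decision rule for declaring mediation.

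Section 12.6.2 describes the power calculation for this hypothesis: "we estimated power focusing on the main effect of the mediator on the outcome". Its one effect size is a "moderate correlation between the hypothesized mediators and the outcome", put at r = 0.2 to 0.3. It concludes that "the estimated power to detect the mediation effect is $0.76-0.99", two-tailed at alpha 0.05. It assumes no treatment effect on any mediator, and section 12.6.3 only refers back to 12.6.2.

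The same section says the trial is powered on the primary hypothesis. It voices concern about low power for mediators, and it gives effect size more weight than p-values for the secondary hypotheses.

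**The concern.** Mediation of an intervention effect needs two links: the intervention changes the mediator, and the mediator relates to the outcome. The calculation covers only the second, but its result is labelled as power for the whole.

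A variable can correlate with ISI at 0.3 and not be moved by BBT-I at all. The calculation would still assign it power of 0.99, although it mediates nothing.

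What is at stake is how null mediator results are read. Someone who takes 0.76-0.99 at face value could treat a null result as fair evidence against a mechanism, when the trial may simply have been unable to show that the mediator changed. The printed range also sits awkwardly beside the plan's own worry about insufficient power for mediators.

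**Working it through.** **Inputs from section 12.6.2.** r = 0.2 and 0.3; two-sided alpha 0.05 (critical value 1.960); N = 180, 90 per arm. N is stated under Hypothesis 1 and not restated for Hypothesis 3. Mixed-model power for ISI is stated as 0.88 at d = 0.4 and 0.99 at d = 0.6.

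**Step 1: reproduce the stated figure.** Power of a two-sided test of one correlation (Fisher z) = Φ(atanh(r) × √(N − 3) − 1.960), with √177 = 13.304.

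- r = 0.2: 0.2027 × 13.304 − 1.960 = 0.737, power 0.770.
- r = 0.3: 0.3095 × 13.304 − 1.960 = 2.158, power 0.985.

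A noncentral t version gives 0.778 and 0.987. Both are close to the printed 0.76 and 0.99. The printed range is therefore what a test of the mediator-outcome association alone would give, as the plan's own description says.

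**Step 2: what a second requirement does.** Suppose mediation is declared only when both paths are detected. Then P(both detected) ≤ P(mediator-outcome path detected). Mediator-outcome power is a ceiling, reached only if the treatment-to-mediator effect is almost certain to be detected.

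**Step 3: illustration of the distance below the ceiling.** Two assumptions are needed that the plan does not make: both paths must be significant, and the treatment effect on the mediator has a stated size. I use d = 0.4 and 0.6, the ends of the plan's ISI range. Joint power is taken as the product of the two path powers.

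*(a) Single-time-point test.* A two-sample t-test with 90 per arm has power 0.761 at d = 0.4 and 0.980 at d = 0.6.

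- d = 0.4: 0.761 × 0.7695 = 0.586; 0.761 × 0.9845 = 0.749.
- d = 0.6: 0.980 × 0.7695 = 0.754; 0.980 × 0.9845 = 0.9648.

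Simulating the joint rule at N = 180, with the mediator-outcome path adjusted for arm (10,000 runs per cell), gives 0.582 and 0.755 at d = 0.4, and 0.754 and 0.966 at d = 0.6. The product is therefore adequate.

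*(b) Borrowing the plan's mixed-model power.* Suppose the stated ISI power carried over to the mediator, and the printed Hypothesis 3 range is used for the other path.

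- d = 0.4: 0.88 × 0.76 = 0.669; 0.88 × 0.99 = 0.871.
- d = 0.6: 0.99 × 0.76 = 0.752; 0.99 × 0.99 = 0.980.

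| Assumed d, treatment to mediator | (a) Single time point | (b) Plan's ISI power borrowed | Printed |
|---|---|---|---|
| 0.4 | 0.59-0.75 | 0.67-0.87 | 0.76-0.99 |
| 0.6 | 0.75-0.96 | 0.75-0.98 | 0.76-0.99 |

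**The case against.** **The basis is disclosed.** Section 12.6.2 says the calculation focused on the mediator's main effect and repeats r beside the result, so a careful reader can see what was powered. This stands in part, and it is why the point is one of labelling. It does not supply the missing treatment-to-mediator effect, and the sentence that reports the result drops the qualification.

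**The framework may not need two significant tests.** The plan names the McArthur framework but prints no criterion, and its cited sources are not available here. This stands. The both-paths rule is an assumption, and the ceiling argument is conditional on it.

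**The mediators are analysed longitudinally.** The study calendar schedules HRV, saliva, actigraphy, diaries, SBSRS and DBAS at all four assessments, and section 12.5 specifies mixed effects modelling. This also stands. A single-time-point test may understate power on the treatment-to-mediator path, so column (a) cannot be presented as the trial's true mediation power. Column (b) is no firmer, because nothing shows that ISI power applies to cortisol or HRV.

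**Readings the documents do not support.** A reader might infer that the power was miscalculated. It was not: it reproduces as mediator-outcome power.

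A reader might also infer that attrition was ignored, because Hypothesis 1 power is described as "fully accounting for the longitudinal study design and projected attrition rate" and Hypothesis 3 carries no such statement. The silence is missing detail, not proof. The match to N = 180 is close but not exact, so it does not settle the matter. Nor would cutting the sample by the figure assumed for Hypothesis 1 ("resulting in 25% attrition by the 6-month follow-up assessment") describe this plan, which keeps all available cases under maximum likelihood.

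**Conclusion.** The label is wrong as written; the number is not. The range 0.76-0.99 is power to detect a mediator-outcome association of r = 0.2 to 0.3. If a treatment effect on the mediator must also be detected, it is at best an upper bound on power for mediation.

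A reader might take one column of the illustration as the real shortfall. The documents do not support a single figure, because they give neither a mediation criterion nor a treatment-to-mediator effect. On the assumptions shown, the printed range is nearly kept at d = 0.6 and is clearly optimistic at d = 0.4, by an amount that depends on the model.

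The point is minor. Hypothesis 3 is secondary, the basis is partly disclosed, and the plan already favours effect size over p-values for the secondary hypotheses. N and the primary analysis do not depend on it.

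**What to change.** In section 12.6.2:

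1. Relabel 0.76-0.99 as power for the mediator-outcome association at r = 0.2 to 0.3.
2. Add one sentence: where mediation also requires a detected treatment effect on the mediator, power for mediation is no higher than this and depends on the size of that effect.
3. If a mediation power is to be quoted, state the criterion for declaring mediation and the sponsor's assumed treatment-to-mediator effect. Compute the power under that criterion and the planned mixed model. The illustrative figures above are not a substitute.

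Items 1 and 2 cost a few words. Item 3 costs one further calculation and probably a less favourable secondary figure. Sample size, data collection and the primary analysis stay as they are.

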12.6.3 Effect size justification

See above.

12.7 Criteria for future studies

This study is fully powered to determine efficacy of BBT-I versus attention and time-controlled group. Changes on the ISI measure of 6 points constitute clinically meaningful results. If this trial replicates our pilot findings, future studies will focus on dissemination of this intervention via multicenter clinical trials.


APPENDICES**APPENDIX A: Participant Eligibility Checklist**

Protocol Title:	Brief Behavioral Intervention For Insomnia During Chemotherapy
Protocol Number:	
Principal Investigator:	[name]

II. Subject Information:

Subject Name/ID:
Gender:  Male  Female

III. Study Information:

SRC Approved IRB Approved Contract signed

IV. Inclusion/Exclusion Criteria

Inclusion Criteria (From IRB approved protocol)	Yes	No	Supporting Documentation*
1. Be female and have a diagnosis of breast cancer (Stage I-III)			
2. Be scheduled for planned cancer treatment (e.g. chemotherapy or biologics such as herceptin)			
3. Have at least 6 weeks of cancer treatment (e.g. chemotherapy or biologics such as herceptin) remaining			
4. Be at least 21 years of age			
5. Be able to understand written and spoken English			
6. Report sleep disturbance of 8 or greater on the ISI, and report insomnia that began or got worse with diagnosis of cancer or treatment with chemotherapy (to exclude pre-existing, chronic insomnia)			
7. Have a Karnofsky score ≥ 70 to ensure that patients are able to participate in intervention and assessments			
Exclusion Criteria (From IRB approved protocol)			
1. Have an unstable self-reported medical or psychiatric illness (Axis I – current or within the last 5 years) that would make it unsafe or impossible to adhere to the study protocol			
2. Be currently pregnant or nursing			
3. Meet current or within 1 year criteria for current alcohol abuse or dependence			

Behavioral Intervention for Insomnia in Cancer

4. Have a self-reported history of sleep apnea or restless leg syndrome (RLS)			
5. Are unable or unwilling to discontinue anxiolytics within 4 hours of education sessions			
6. Have irregular heartbeats or arrhythmia (self-reported or in the medical record)			

*All subject files must include supporting documentation to confirm subject eligibility. The method of confirmation can include, but is not limited to, laboratory test results, radiology test results, subject self-report, and medical record review.

IV. Statement of Eligibility

By signing this form of this trial I verify that this subject is [**eligible** / **ineligible**] for participation in the study. This study is approved by the Stanford Cancer Institute Scientific Review Committee, the Stanford IRB, and has finalized financial and contractual agreements as required by Stanford School of Medicine’s Research Management Group.

Study Coordinator Signature:	Date:
Printed Name:
